5.3 Method for Assigning Subjects to Treatment Groups

Each group (or dose level) will enroll and after 4 weeks of follow up of 3 patients treated with ixazomib at a particular dose will be reviewed for safety by DSMB before initiating enrollment into the next group (or dose level). All patients in the current cohort must have completed 4 weeks and the cohort's data reviewed by the by the Safety Monitoring Committee before patients in the next cohort can receive drug. Patients from the next cohort may complete the first two visits prior to DSMB review of earlier cohorts.

Dose limiting toxicities are defined in Section 6.17 Table 2. After all the subjects in each dosing group has completed Cycle 1 of ixazomib, the DSMB may recommend:

- (i) Proceed to next dose level, or
- (ii) Terminate trial, or
- (iii) Enroll a replacement subject for a withdrawn subject, or
- (iv) Add 5 more patients at previous dose group (maximum tolerated dose). The maximum tolerated dose is that level where no more than 0 out of 3 patients experience dose limiting toxicity.

If no DLT are observed in 3 subjects, the next dosing level will be initiated.

After DSMB review of the 4 mg dosing level, if no DLT are observed, the DSMB may recommend:

- (i) Terminating the trial
- (ii) Enroll 5 more patients at the maximum tolerated dose.

The NNRTIs etravirine and efavirenz are moderate CYP3A enzyme inducers and have potential to decrease systemic exposure to ixazomib. That possibility will be explored by measuring trough ixazomib levels in all patients and comparing ixazomib concentrations in patients on different ART regimens. The DSMB will have to consider the number of patients treated with NNRTIs in a particular group as the safety profile of a group may be underestimated if the majority of patients are treated with NNRTIs as part of their ARV regimen.

Additional data review by the DSMB will occur after Day 84 for each dosing cohort. At this time, the DSMB may recommend:

[figure not shown]
- (i) Proceed to uninterrupted weekly dosing on days 1, 8, 15 and 22 of a 28 day cycle, or
- (ii) Continue previous dosing on days 1, 8, and 15 of a 28 day cycle, or
- (iii) Enroll a replacement subject for a withdrawn subject, or
- (iv) Terminate dosing.

This determination will be made on an individual participant basis, and not a dosing cohort basis, and will be made based on the presence or absence of adverse drug effects that do not meet the definition of dose related toxicities.

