Study Product, Dose, Route, Regimen	
Patients will be treated in sequential groups after the safety evaluation of each group by the DSMB as follows:
 
Group 1: 3 patients with HIV infection, who meet inclusion criteria, will receive ixazomib 1 mg on days 1, 8 and 15 for three 28 days cycles, then be reviewed by DSMB and based upon their recommendation patients will receive either (i) ixazomib once weekly for 12 weeks or (ii) ixazomib 1 mg on days 1, 8 and 15 for three 28 days cycles. Visits 3-15 will have a window of ± 3 days.
 
Group 2: 3 patients with HIV infection, who meet inclusion criteria, will receive ixazomib 2mg on days 1, 8 and 15 for three 28 days cycles, then be reviewed by DSMB and based upon their recommendation patients will receive either (i) ixazomib once weekly for 12 weeks or (ii) ixazomib 2 mg on days 1, 8 and 15 for three 28 days cycles. Visits 3-15 will have a window of ± 3 days.
 
Group 3: 3 patients with HIV infection, who meet inclusion criteria, will receive ixazomib 3 mg on days 1, 8 and 15 for three 28 days cycles, then be reviewed by DSMB and based upon their recommendation patients will receive either (i) ixazomib once weekly for 12 weeks or (ii) ixazomib 3 mg on days 1, 8 and 15 for three 28 days cycles. Visits 3-15 will have a window of ± 3 days.
 
Group 4: 3 patients with HIV infection, who meet inclusion criteria, will receive ixazomib 4 mg on days 1, 8 and 15 for three 28 days cycles, then be reviewed by DSMB and based upon their recommendation patients will receive either (i) ixazomib once weekly for 12 weeks or (ii) ixazomib 4 mg on days 1, 8 and 15 for three 28 days cycles. Visits 3-15 will have a window of ± 3 days.
 
Group 5: 5 patients with HIV infection, who meet inclusion criteria will receive the maximum tolerated dose of ixazomib per DSMB recommendations. Visits 3-15 will have a window of ± 3 days.

Duration of Treatment Administration for Each Patient	24 weeks
Reference therapy	None

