1.5 Dose Rationale and Risk/Benefits

Safety is our first concern, therefore we have chosen a dose escalation study, starting at a low dose with regular and frequent DSMB safety review. The lowest starting dose in this study is 1 mg weekly, which is expected to achieve <30% 20S proteasome inhibition based on previously published pharmacodynamics data in advanced non-hematologic malignancies (Invest New Drugs. 2015; 33(3): 652–663). The maximum possible dose of ixazomib to be administered in this trial is similar to the doses [name] et al. have previously used in a Phase I study of weekly ixazomib for relapsed/refractory multiple myeloma (60). However, during that study, dosing was BSA based, and the maximum tolerated dose was 2.97 mg/m² (translating to a fixed dose of 5.5 mg). The estimated half-life of ixazomib was 3.6 to 11.3 days, supporting weekly dosing, which is the dosing schedule studied in Phase 2 and 3 trials, and ultimately approved by the FDA for treatment of multiple myeloma.

Furthermore, the doses of ixazomib to be administered in this trial are expected to correlate with the concentrations used in the preliminary data noted above. Maximum biologic effects were noted in the in vitro and ex vivo experiments above with a single treatment of 100 nM ixazomib, which corresponds to a peak in vitro concentration of 36.1 ng/ml. In Study C16009, Arm 3, adult patients with a diagnosis of an advanced non-hematologic malignancy or lymphoma were treated with a standard 4 mg oral dose of ixazomib, and geometric mean C_{max} in the fasted state was 77 ng/ml with a 57% CV. Therefore, the proposed dose range for this study (from 1 to 4 mg) is expected to result in plasma C_{max} values that approximate the doses used in the in vitro studies. C_{min} and C_{max} levels before and after the second dose of ixazomib on Day+15 will be measured.

Potential Risks of ixazomib: Because ixazomib has not been previously studied in HIV infected patients or otherwise healthy individuals, it is unclear what side effects low doses of ixazomib

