Additional details on the potential risks of ixazomib may be found in the current IB.

Potential Benefits of ixazomib: It is likely that individual participants in this phase I/IIa study will derive no direct clinical benefit from treatment with ixazomib, as specified in the informed consent form.

The hypothesis we are exploring based on in vitro and ex vivo data is that therapy with ixazomib decreases cell-associated HIV DNA by 1) inducing HIV reactivation, 2) increasing expression of pro-apoptotic Casp8p41 in HIV-infected cells, and 3) inducing cell death specifically in HIV-infected cells while sparing HIV-uninfected cells. If these positive effects are recapitulated when treating patients with HIV on antiretroviral therapy with ixazomib, this would represent the first clinical intervention found to decrease the size of the HIV reservoir, which is the main barrier to HIV cure.

There is an urgent need for an HIV cure. While patients with HIV on antiretroviral therapy live longer and have reduced rates of opportunistic infections and malignancies compared to untreated HIV patients, data suggest that life expectancy for patients with treated HIV in the current treatment era are still nearly 14 years shorter than age and sex-matched uninfected controls (Marcus et al. *J Acquir Immune Defic Syndr*. 2016 Mar 29), indicating persistent increased mortality even in treated patients. Chronic, treated HIV infection is associated with abnormal chronic inflammation, cardiovascular disease, metabolic syndrome, bone disease, neurocognitive defects and age-related non-AIDS malignancies. Furthermore, current HIV treatments require lifelong therapy with antiretroviral medications, which have substantial associated burdens of costs and adverse drug effects themselves.

Therefore, establishment of a maximal tolerated dose, and obtaining preliminary efficacy data at reducing HIV reservoir size, will inform future therapeutic study designs with the intent of establishing whether ixazomib has beneficial effects in patients with HIV infection.

2 Study Objectives

Primary Objective

To determine the safety and tolerability of ixazomib in HIV infected patients who are on a stable regimen of ART that suppresses HIV replication (HIV RNA to undetectable levels using clinical assays).

Secondary Objectives

To determine the effect of ixazomib on:

- 1) Change in cell associated HIV DNA in CD4 T cell subsets from Week -1 to Week 24;

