5.2 Treatment Regimen

Patients will be treated in sequential groups after the safety evaluation of each group by the DSMB. Visits 1 and 2 do not have a time window, and can occur without DSMB review as patients will not receive drug at those visits. The following groups will be studied in this protocol:

Group 1: 3 patients with HIV infection, who meet inclusion criteria, will receive ixazomib 1 mg on days 1, 8 and 15 for 28 days. After 28 days, the DSMB will meet to decide if enrollment of the next cohort should proceed. After 84 days (28 days x 3 cycles), the DSMB will meet and decide if patients will receive either (i) ixazomib once weekly for 12 weeks or (ii) ixazomib 1 mg on days 1, 8 and 15 for an additional three 28 days cycles. Visits 3-15 will have a window of \pm 3 days.

Group 2: 3 patients with HIV infection, who meet inclusion criteria, will receive ixazomib 2 mg on days 1, 8 and 15 for 28 days. After 28 days, the DSMB will meet to decide if enrollment of the next cohort should proceed. After 84 days (28 days x 3 cycles), the DSMB will meet and decide if patients will receive either (i) ixazomib once weekly for 12 weeks or (ii) ixazomib 2 mg

on days 1, 8 and 15 for an additional three 28 days cycles. Visits 3-15 will have a window of ± 3 days.

[figure not shown]
Group 3: 3 patients with HIV infection, who meet inclusion criteria, will receive ixazomib 3 mg on days 1, 8 and 15 for 28 days. After 28 days, the DSMB will meet to decide if enrollment of the next cohort should proceed. After 84 days (28 days x 3 cycles), the DSMB will meet and decide if patients will receive either (i) ixazomib once weekly for 12 weeks or (ii) ixazomib 3 mg on days 1, 8 and 15 for an additional three 28 days cycles. Visits 3-15 will have a window of ± 3 days.

Group 4: 3 patients with HIV infection, who meet inclusion criteria, will receive ixazomib 4 mg on days 1, 8 and 15 for 28 days. After 28 days, the DSMB will meet to decide if enrollment of the next cohort should proceed. After 84 days (28 days x 3 cycles), the DSMB will meet and decide if patients will receive either (i) ixazomib once weekly for 12 weeks or (ii) ixazomib 4 mg on days 1, 8 and 15 for an additional three 28 days cycles. Visits 3-15 will have a window of ± 3 days.

Group 5: 5 patients with HIV infection, who meet inclusion criteria will receive the maximum tolerated dose of ixazomib as determined by DSMB recommendation. Visits 3-15 will have a window of ± 3 days.

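### The MTD definition in 5.3 does not require that a higher dose failed, so if 4 mg clears, the plan speaks of a maximum tolerated dose that the data could not show

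*Combined protocol and SAP*

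**What the plan says.** The trial escalates through 1, 2, 3 and 4 mg with three patients per level, and five further patients form Group 5 (section 5.2 and Study Summary). No level above 4 mg is planned.

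Section 5.3 gives the definition: "The maximum tolerated dose is that level where no more than 0 out of 3 patients experience dose limiting toxicity". Three clear patients lead to the next level. Among the DSMB's options after a cohort review is "Add 5 more patients at previous dose group (maximum tolerated dose"), which places the MTD one step below the level under review.

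A separate rule covers the top level: "After DSMB review of the 4 mg dosing level, if no DLT are observed, the DSMB may recommend" either termination or "Enroll 5 more patients at the maximum tolerated dose".

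Group 5, in section 5.2, "will receive the maximum tolerated dose of ixazomib as determined by DSMB recommendation"; the Study Summary says the same in nearly the same words ("will receive the maximum tolerated dose of ixazomib per DSMB recommendations").

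Section 1.5 gives the label a use: "establishment of a maximal tolerated dose, and obtaining preliminary efficacy data at reducing HIV reservoir size, will inform future therapeutic study designs". The same section reports a weekly phase 1 study in myeloma whose MTD was 2.97 mg/m², "translating to a fixed dose of 5.5 mg", and a monotherapy trial in lymphoma that escalated through 4, 5.3 and 7 mg.

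**The concern.** An MTD is normally bounded on both sides: the level itself is tolerated and the next one up is not. The definition in 5.3 supplies only the first half. When escalation stops on a DLT, the reference to the previous dose group supplies the second half in practice. When 4 mg clears, nothing does. No level has failed and none higher will be tried, yet the expansion option still uses the term.

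At stake is how the dose result is read later. A designer told that the MTD in people with HIV on ART was 4 mg would take this as an observed toxicity limit. The trial would have shown only that escalation reached a ceiling fixed in advance.

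**Working it through.** **Plan's own figure.** Four levels of three plus five in Group 5: 4 × 3 + 5 = 17, the stated maximum. The figure reproduces and does not depend on how the MTD is defined.

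**Paths through 5.3.**

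| First level with a DLT | Dose called MTD | Failed level above it? |
|---|---|---|
| 1 mg | none (no lower level) | – |
| 2 mg | 1 mg | yes, 2 mg |
| 3 mg | 2 mg | yes, 3 mg |
| 4 mg | 3 mg | yes, 4 mg |
| none | a dose recommended by the DSMB | no |

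Only the last row is a problem. There 1, 2, 3 and 4 mg all meet the 0/3 criterion, so the definition does not single out one dose. It points to 4 mg only if *maximum* is taken to mean the highest cleared level.

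**How often the last row could occur.** The documents give no DLT rates for this population, so the rates below are assumptions. P(all four levels clear) = [(1−p₁)(1−p₂)(1−p₃)(1−p₄)]³.

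- 1/2/3/5%: 0.894³ = 71%
- 2/5/8/10%: 0.771³ = 46%
- 5/10/15/20%: 0.581³ = 20%
- 5/10/20/30%: 0.479³ = 11%

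This is the chance of reaching the branch, before the DSMB chooses whether to expand and at which dose. It is not the chance that anyone is misled.

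**What the data at 4 mg could then say.** One-sided 95% upper bounds on the DLT rate p:

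- Cohort only, 0/3: solve (1−p)³ = 0.05, so p = 1 − 0.05^(1/3) = 63%.
- Cohort plus Group 5 treated at 4 mg. Expansion there happens only after 0/3, so x DLTs in total is not a plain binomial count out of 8. Ordering outcomes by the two stages, solve (1−p)³ × P(Bin(5, p) ≤ x) = 0.05.

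| DLTs in Group 5 (after 0/3) | Two-stage bound | Simple pooled binomial bound, x/8 |
|---|---|---|
| 0 | 31% | 31% |
| 1 | 44% | 47% |
| 2 | 52% | 60% |

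The pooled column is the 0.95 quantile of Beta(x+1, 8−x). It ignores the stopping rule and is conservative for x = 1 and 2. The two agree at x = 0 because both reduce to (1−p)⁸ = 0.05.

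**A DLT in Group 5.** If the dose is 4 mg, P(at least one DLT in 5) = 1 − (1−p)⁵, which is 23%, 41%, 67% and 83% for assumed rates of 5%, 10%, 20% and 30%. The definition, written for three patients, does not say what becomes of the label then.

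**The case against.** The strongest reply is that this is terminology with little downstream effect. The MTD is not a listed objective, endpoint or analysis. Safety is reported descriptively by dose group and CTC grade (section 7.2), so later designers would see the toxicity at 4 mg whatever the label. Section 1.5 openly gives the dose range as 1 to 4 mg, so the cap is visible, and 5.3 can be read as a working definition for this trial. All of this stands, and it limits the point to a minor one. It does not supply the missing condition, and section 1.5 still gives the MTD a role in later designs.

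The text is also incomplete. Section 5.2 announces a list of DSMB recommendations that does not follow there, figures in 5.2 and 5.3 are not shown, and the DSMB charter and its analysis plan (section 9.4.1) are not supplied. A provision for an MTD that was not reached may exist in one of these. Even so, the definition printed in 5.3 should agree with it.

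Two stronger readings are tempting and are not supported.

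- A reader might infer that the protocol declares 4 mg to be the MTD. No sentence does so. The DSMB may terminate, or may choose a lower cleared level for Group 5.
- A reader might infer from the 5.5 mg figure and the lymphoma doses that 4 mg lies below the true limit here. Those populations differ and their DLT criteria are not given. The citations show only that 4 mg is a planned ceiling and that higher doses have been studied elsewhere.

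**Conclusion.** The point holds as a minor defect in the definition. As written in 5.3, the MTD is any level with 0/3 DLTs, and on the branch where 4 mg clears the plan uses the term with no failed level above. The supportable conclusion there is that the highest planned dose was cleared, with a DLT rate at 4 mg bounded only at 63% after 0/3, or at 31%, 44% or 52% after 0, 1 or 2 DLTs among five Group 5 patients treated at 4 mg.

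The label falls on 4 mg only if all four levels clear, the DSMB expands, and it selects 4 mg. The 11% to 71% range for the first condition rests on assumed rates and does not measure the size of the defect. Patient safety, the maximum of 17 and the descriptive safety analysis are unaffected. The reading rests on the visible text.

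**What to change.** - **Section 5.3.** Define the MTD as the highest level with 0 of 3 DLTs when the next tested level had at least one DLT. State that if 4 mg clears, the result is reported as *MTD not reached; highest planned dose 4 mg*.
- **Section 5.2 and Study Summary.** Describe Group 5 as expansion at the cleared level that the DSMB selects.
- **Safety reporting (section 7.2).** Give the DLT count at the expansion level separately for the escalation cohort and for Group 5, so that a DLT in Group 5 is visible. An upper bound is optional. If one is added, use the two-stage bounds shown above, or label the pooled binomial bounds (31%, 47%, 60%) as conservative and not exact. Recompute for the actual counts.

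The cost is a few sentences and at most one added descriptive interval. Doses, sample size and DSMB authority do not change. The downside is a more modest dose conclusion if 4 mg clears.

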4.4 Early Withdrawal of Subjects

4.4.1 When and How to Withdraw Subjects

Permanently discontinue ixazomib in individual subjects if any of the following occur:

- Death of any subject
- Anaphylactic reaction in any subject
- A life-threatening adverse event in any subject
- Any Grade 3 AE (except if there is clear evidence that it is not study drug related – i.e. a plausible alternative reason).
- Any Grade 4 AE
- A decrease in CD4 count below 350 cells/mm³, confirmed on repeat testing within 2 weeks, and associated with a relative drop in CD4 T cell percentage by >25% from baseline values, in the absence of an alternative explanation
- Confirmed virologic rebound (HIV-1 RNA >500 copies/ml confirmed by a second assay done within 14 days of the initial one). If the HIV-1 viral load is >20 copies/mL and <500 copies/mL, the HIV-1 viral load will be rechecked every 2 weeks until it becomes <20 copies/mL or >500 copies/mL.
- Development of \geq Grade 1 peripheral neuropathy with or without pain

An independent Data Safety and Monitoring Board will review the case. The committee and principal investigators will determine whether there is an association between the event and the ixazomib. The DSMB will make a recommendation accordingly as to whether the study should proceed, or if a modification in trial design is required, or if a replacement subject should be enrolled at the same dose as the withdrawn subject.

Reasons for early withdrawal of individual subjects may include:

- Subjects refuse to return for any remaining study visits.
- Subjects discontinue the ixazomib at any time during the study.
- Safety reasons, either at the discretion of the Investigator or at the subject's request.
- Protocol violations at the discretion of the principal investigators.
- Initiation of concomitant therapy that could interfere with the results of the study or ixazomib
- Subject's decision to withdraw, at any time.

All subjects are free to withdraw from participating in this study at any time and for whatever reason, specified or unspecified, and without prejudice.

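### A permanent stop for CD4 loss under section 4.4.1 is not named as a DLT, so a dose level with such a stop graded below 3 can still meet the written 0-of-3 rules for escalation and the MTD

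*Combined protocol and SAP*

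**What the plan says.** In the combined protocol and SAP, section 5.3 bases dose-finding on a DLT count among three participants per level. It defines the MTD thus: "The maximum tolerated dose is that level where no more than 0 out of 3 patients experience dose limiting toxicity". On escalation it says: "If no DLT are observed in 3 subjects, the next dosing level will be initiated". For the definition it points elsewhere: "Dose limiting toxicities are defined in Section 6.17 Table 2". A separate list of dose-limiting toxicities in section 6, after the text on neuropathy screening, has three items: Grade 4 or higher, Grade 3 unless clearly unrelated to the drug, and neuropathy of Grade 1 or higher.

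Section 4.4.1 lists the events that end ixazomib permanently for a participant. One is a CD4 count below 350 cells/mm³ that a repeat test bears out no more than 2 weeks later, provided it is also "associated with a relative drop in CD4 T cell percentage by >25% from baseline values, in the absence of an alternative explanation". The same list stops treatment for neuropathy from "Grade 1 peripheral neuropathy with or without pain" upward. Section 9.3 lists any CD4 count below 350 among its stopping rules, with no need for confirmation.

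After a 4.4.1 event the DSMB reviews the case and may recommend, among other things, "if a replacement subject should be enrolled at the same dose as the withdrawn subject". Section 5.2 gives Group 5 the "maximum tolerated dose of ixazomib as determined by DSMB recommendation".

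**The concern.** The protocol treats confirmed, unexplained CD4 loss as serious enough to end treatment, yet does not name it among the events that decide whether a dose was tolerated. Neuropathy of Grade 1, which Appendix I describes as asymptomatic, fails a dose level. A CD4 stop graded below 3 does not.

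The population has HIV, safety and tolerability are the primary objective, and section 1.3 names lymphoid cell depletion among the potential risks seen in animals. Section 1.5 says that "establishment of a maximal tolerated dose, and obtaining preliminary efficacy data at reducing HIV reservoir size, will inform future therapeutic study designs". An MTD labelled 0 of 3 at a level where someone was taken off the drug for CD4 loss would give later designers a misleading figure.

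**Working it through.** **Setting the sections side by side**

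| Event that ends treatment under 4.4.1 | Section 6 DLT list | Table 2 (6.17) | Section 9.3 |
|---|---|---|---|
| Grade 3 AE, unless clearly unrelated | yes | yes | yes |
| Grade 4 AE | yes | yes | yes |
| Neuropathy, Grade 1 or higher | yes | yes (row written for Grade 1) | no |
| Confirmed HIV RNA above 500 copies/mL | no | yes | yes |
| CD4 below 350, confirmed, with percentage fall | **no** | **no** | yes (any count below 350) |

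CD4 loss is the only one of these five that appears in neither DLT source. Under section 8.1 a laboratory value that leads to discontinuation is an AE, so a CD4 stop graded 3 or higher is already a DLT through the general items. The gap is limited to stops graded below 3.

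**Planned sample size.** Four levels of 3 plus 5 at the MTD: 4 × 3 + 5 = 17, which matches the stated maximum. The documents give no error rate for the 0-of-3 rule.

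**Size of the event.** Entry needs a CD4 count of at least 500 (section 4.1). The smallest fall that reaches 350 is (500 − 350)/500 = 30%, so a count below 350 is a fall of more than 30%.

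**Effect on the count.** One CD4 stop among three participants, with no other DLT:
- counted: 1 of 3, so the level fails, and under option (iv) of 5.3 the MTD is the previous level;
- not counted: 0 of 3, so the level passes;
- with a replacement enrolled: 1 of 4 if the event counts and the stopped participant is kept, 0 of 3 if that participant is dropped. Sections 4.4.1 and 5.3 do not say which applies.

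**Effect on the stated MTD**, where the level with the uncounted stop is the one declared the MTD:
- 4 mg instead of 3 mg: 4/3 = 1.33, or 33% higher;
- 3 mg instead of 2 mg: 3/2 = 1.50, or 50% higher;
- 2 mg instead of 1 mg: 2/1 = 2.00, or 100% higher.

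**Timing.** Section 6 schedules CD4 counts on treatment at Weeks 3, 4, 8, 12, 16 and 20. Two of these six fall by the 4-week review that governs escalation.
- A low count at Week 3 has a scheduled repeat at Week 4, at most 7 + 6 = 13 days later with the ±3-day windows, so inside the 2-week limit.
- A low count at Week 4 is next scheduled for testing at Week 8, 28 − 6 = 22 to 28 + 6 = 34 days later. It needs an unscheduled repeat and could still be unconfirmed at the review.

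**The case against.** The strongest reply is that the DSMB already covers this. It reviews every 4.4.1 event and judges association with ixazomib, decides escalation (sections 7.2 and 9.4.1), may recommend termination even after a clean 4 mg level, and recommends the Group 5 dose. Section 9.3 brings any CD4 count below 350 to the committee without waiting for a repeat. The event also stays in the safety results: AEs are described by grade and dosing group for everyone with at least one dose. All of this stands. It limits the consequence but does not change what the written count says.

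The DSMB charter is not among the documents, and the list of recommendations at the end of section 5.2 is not visible. Either might deal with CD4 loss.

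Several stronger readings are tempting, and the documents do not support them:
- *The trial would escalate automatically past a CD4 stop.* The DSMB's role rules this out.
- *Listing CD4 apart from Grade 3 and Grade 4 in 4.4.1 shows that those items do not cover it.* Death and life-threatening events are also listed separately there, so separate listing proves nothing about grade.
- *CD4 was singled out while HIV RNA was made a DLT.* The section 6 list omits both. Section 5.3 does point to Table 2 for the definition, but that table governs dose changes and also holds low-grade rash, so a row in it does not settle DLT status.
- *The MTD is the trial's main product.* Section 1.5 says only that it will inform later designs; the objectives in section 2 are safety and tolerability, then reservoir and immune measures.
- *The gap has a calculable probability.* No rate of CD4 stops is given, so any figure would only restate an assumed rate.

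It can also be argued that leaving CD4 loss to individual stopping plus expert review is a reasonable choice, since under a 0-of-3 rule one chance fall fails a level. That is a real cost. The confirmation, percentage and no-other-explanation conditions already reduce it.

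**Conclusion.** The point holds as a flaw in the written DLT and MTD rule, and correcting it is a cheap improvement. A participant can be permanently stopped for confirmed, unexplained CD4 loss while the level still meets both the escalation sentence and the MTD definition in 5.3. The MTD under that rule can then stand one level, 1 mg, above what it would be if the stop were counted.

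This rests on one assumption: that at least some 4.4.1 CD4 stops would be graded below 3. The documents do not give the CTCAE cut-points for CD4 count, so they can neither confirm nor exclude it. If every such stop were Grade 3 or higher, the general items would already capture it, and the change would only make that explicit. No likelihood is attached, and the DSMB may choose a lower Group 5 dose whatever the count reads.

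**What to change.** Three changes:

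1. Add to the section 6 DLT list: *Permanent discontinuation under the Section 4.4.1 CD4 criterion, unless the DSMB determines it is not associated with ixazomib.*
2. Add the matching row to Table 2 in section 6.17, beside the HIV RNA row, with permanent discontinuation as the action.
3. Add to section 5.3: *A participant who is replaced after a DLT stays in that level's DLT count.*

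A formal hold on escalation while a low CD4 count awaits its repeat is optional, because section 9.3 already refers any count below 350 to the committee. If adopted, it would delay the next level by at most the 2 weeks that 4.4.1 allows for the repeat.

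The cost is one list item, one table row and one sentence, with no new test. The downside is that a chance CD4 fall may occasionally count as a DLT and lower the MTD by one level. The repeat test, the percentage criterion and the DSMB's judgement of association limit that.
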